followed through the end of the study, including those who seek alternative treatment or retreatment to ensure that all safety/adverse events are captured. See Timeline Table 5.	

Table 5. Timeline of Events

				TIMELIN	IE OF MI	EASURE	S							
MEASURE	SCREEN	BASE LINE	PERI OP	6 WK	6M	12 M	18 M	24 M	30 M	36 M	42 M	48 M	54 M	60 M
Window (+/- wk)				-1wk / +2wks	+/- 6wks									
Eligibility/ Consent	Х													
Demographics	X													
Medical History	Х													
Randomization		Χ												
Physical Exam (height, weight and PVR)		Х												
Surgeon's Report and Hospitalization			X											
POP-Q for Inclusion Criteria Unmasked Staff		Х												
Study Surgery Status			X											
6 Week Unmasked Evaluator				X										
Assessment														
(includes Complications														
Assessment)														
6 Week Postoperative				X										
Recovery Assessment														
6-60 Month Masked Evaluator Assessment (includes POP-Q and Complications Assessment)					X	X	X	X	X	X	X	X	X	X
Retreatment and					X	X	X	X	X	X	Х	X	X	X
Complications Assessments Unmasked (6-60 month visit form)							^							^
AE Review			Х	Х	Х	Х	X	Х	Х	Х	Х	Х	Х	Х
Exams for Mesh Exposure				Х	X	X	Х	Х	X	X	X	X	Х	X
Non-Pain Med Collection		Χ	Χ	Χ	X	Х	Х	X	X	Χ	Х	X	Х	X
Catheterization Follow-Up*	Q 2 weeks if need for continuous catheterization post 6-Week Visit													
Functional Activity Scale		Χ			X	X		X		Х		X		X
Surgical Pain Scale		Χ		Χ	Χ	Χ		Χ		Χ		X		X
Body Part Pain Score		X		X	X	Х		X		Х		X		X

	TIMELINE OF MEASURES													
MEASURE	SCREEN	BASE LINE	PERI OP	6 WK	6M	12 M	18 M	24 M	30 M	36 M	42 M	48 M	54 M	60 M
Window (+/- wk)				-1wk / +2wks	+/- 6wks									
PFDI-20 (includes POPDI-6, CRADI-8, UDI-6)	Х				X	X		Х		X		X		Х
PFDI-20 Question 3 Only							X		X		X		X	
PFIQ-7		X			X	X		X		X		X		X
PGI-I					X	X		X		X		X		X
PISQ-IR		X			Х	X		Х		Х		X		X
BIPOP		X			Х	X		Х		Х		Х		Х
SF-12		Χ			Х	Χ		Х		Х		Х		Χ
DRS-PFD/SDS-PFD						X		Х		Х				

^{*}If 6 Week Post-Operative Visit indicates that participant requires continued catheterization, complete this every 2 weeks until catheterization ends

L. DESCRIPTION OF OUTCOME MEASURES

The following outcome measures will be collected at baseline, 6 months, 12 months, and then every 6 months with the survival analysis approach.

L.1. Primary Outcome Measure

The participant will be considered a treatment failure if any ONE of the following criteria is met:

- 1. Report of bothersome vaginal bulge symptoms (see definition below), or

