				0 = No, else if subject attended at least one post- operative visit 6 months or after and reported no additional treatment for urinary incontinence was performed for question A4 across all attended post-operative visits. Subjects with missing responses to question A4 are included as long as the subject has at least one non-missing response (assuming low missing response rate among attended visits).
				. = Missing, otherwise

Anatomic POPQ point Ba measurement	CRF-12	Continuous	6-, 12-, 18-, 24-, 30-, 36-, 42-, 48-, 54-, 60- months	At each timepoint, POPQ point Ba as reported on the evaluator (blinded) follow-up CRF-12 during POPQ examination at the timepoint's corresponding attended post-operative visit.
Anatomic POPQ point Bp measurement	CRF-12	Continuous	6-, 12-, 18-, 24-, 30-, 36-, 42-, 48-, 54-, 60- months	At each timepoint, POPQ point Bp as reported on the evaluator (blinded) follow-up CRF-12 during POPQ examination at the timepoint's corresponding attended post-operative visit.
Anatomic POPQ point C measurement	CRF-12	Continuous	6-, 12-, 18-, 24-, 30-, 36-, 42-, 48-, 54-, 60- months	At each timepoint, POPQ point C as reported on the evaluator (blinded) follow-up CRF-12 during POPQ examination at the timepoint's corresponding attended post-operative visit.
Anatomic POPQ point GH measurement	CRF-12	Continuous	6-, 12-, 18-, 24-, 30-, 36-, 42-, 48-, 54-, 60- months	At each timepoint, POPQ point GH as reported on the evaluator (blinded) follow-up CRF-12 during POPQ examination at the timepoint's corresponding attended post-operative visit.
Anatomic POPQ point Aa measurement	CRF-12	Continuous	6-, 12-, 18-, 24-, 30-, 36-, 42-, 48-, 54-, 60- months	At each timepoint, POPQ point Aa as reported on the evaluator (blinded) follow-up CRF-12 during POPQ examination at the timepoint's corresponding attended post-operative visit.
Anatomic POPQ point Ap measurement	CRF-12	Continuous	6-, 12-, 18-, 24-, 30-, 36-, 42-, 48-, 54-, 60- months	At each timepoint, POPQ point Ap as reported on the evaluator (blinded) follow-up CRF-12 during POPQ examination at the timepoint's corresponding attended post-operative visit.
Anatomic POPQ point Pb measurement	CRF-12	Continuous	6-, 12-, 18-, 24-, 30-, 36-, 42-, 48-, 54-, 60- months	At each timepoint, POPQ point Pb as reported on the evaluator (blinded) follow-up CRF-12 during POPQ

				examination at the timepoint's corresponding attended post-operative visit.

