				0 = No, else if subject attended at least one post-operative visit 6 weeks or after and complication(s) of interest specified above are reported as "Not Evident" across all attended post-operative visits. Subjects with missing responses are included as long as the subject has at least one "Not Evident" response (assuming low missing response rate among attended visits).
Indicator of prolapse mesh exposure in the apex of vagina	CRF-8, CRF- 10/12, AE log	Binary	Post-surgery through last visit	
 
Missing, otherwise
 
Through the timepoint of follow-up, the indicator is defined as follows:
 
1 = Yes, if mesh exposure in vagina is reported as evident (i.e. response of "AE", "SAE") and apex=Yes and Description of Management of Mesh Exposure indicates the mesh was "from/for Prolapse Surgery" (case insensitive) on any of the complication tables as described above
 

				0 = No, else if subject attended at least one post-operative visit 6 weeks or after and complication(s) of interest specified above are reported as "Not Evident" across all attended post-operative visits. Subjects with missing responses are

				<pre>included as long as the subject has at least one "Not Evident" response (assuming low missing response rate among attended visits).</pre> . = Missing, otherwise
Indicator of prolapse mesh erosion (exposure into adjacent organs)	CRF-8, CRF- 10/12, AE log	Binary	Post-surgery through last visit	Through the timepoint of follow-up among subjects who received the hysteropexy surgical intervention as reported on the surgeon's report CRF-8 (i.e. response to question A8 is "Uphold Lite"), based on the systematic collection of open-ended adverse events as reported on the AE log with an onset start date on or after the date of surgical intervention and based on the specific complications as reported on the evaluator (blinded) follow-up CRF-10/12 collected at 6-weeks and in 6-month intervals through 5 years, the indicator is defined as follows:
				1 = Yes, if mesh erosion into viscera (urethra, bladder, ureter, rectum, or bowel locations) is reported as evident (i.e. response of "AE", "SAE") on any of the complication tables as described above

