				(0=not bad at all,, 10=most intense bad feeling imaginable). If the question is missing a response, then the score is not calculated. The outcome will then be computed as the difference in score at each timepoint's corresponding attended post-operative visit and the score at baseline. If data for the assessment are missing at a timepoint's corresponding attended post-operative visit, the outcome variable will be coded as missing.
Change from baseline in body part pain score BPPS score**	SPS	Continuous	6-weeks thru last visit	The BPPS score will be computed at baseline and at each timepoint's corresponding attended post-operative visit during which assessments are administered and collected using standard scoring algorithms (TOMUS study). Specifically, average the responses for questions Q1 through Q7 (0=no or yes: no pain,, 10=yes: most intense). If there are missing responses, then the score is the average of the non-missing responses. The outcome will then be computed as the difference in score at each timepoint's corresponding attended post-operative visit and the score at baseline. If data for the assessment are missing at a timepoint's corresponding attended post-operative visit, the outcome variable will be coded as missing.
Maximum modified Dindo score across all complications And indicator for the Maximum modified Dindo score ≥ grade III	CRF-8, CRF-9, CRF- 10/12, CRF-11, CRF-13	Ordinal Categorical (11 levels)	6-weeks thru last visit	Through the timepoint of follow-up, based on the single Dindo score for the most severe complication as reported on the surgeon's report (unblinded) CRF-8, hospitalization CRF-9, evaluator (blinded) follow-up CRF-10/12 collected during surgery, during hospitalization, and at 6- weeks and in 6-month intervals through 5 years respectively, and as reported on the coordinator post-operative CRF-11, and coordinator follow-up CRF-13 collected at 6-weeks, and in 6-month intervals through 5 years respectively, the maximum of the Dindo scores (0.0=no complications, 1.0=grade I, 2.1=grade IIa, 2.2=grade IIabx, 2.3=grade IIb, 3.1=grade IIIo, 3.2=grade IIIa, 3.3=grade IIIb, 4.1=grade IVa, 4.2=grade IVb, 5.0=grade V) is taken excluding Dindo scores reported for granulation tissue, suture exposure, and/or suture erosion complications reported ≤ 12 weeks from surgical intervention (i.e. surgery and 6-week visits) on any of the complication tables as described above.

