				If a subject reported no complications, then their maximum Dindo score will be assigned a value of 0.0=no complication. A missing maximum Dindo score is assigned to subjects who discontinued prior to their surgical intervention visit.
				Then, the indicator for maximum Dindo score ≥ grade III is defined as follows:
				1 = Yes, if the maximum of the Dindo scores as described above is $\geq$ grade III (i.e. score $\geq$ 3.1).
				0 = No, else if the maximum of the Dindo scores as described above is < grade III (i.e. score < 3.1).
				. = Missing, otherwise
				*Note: Prior to final database lock, a listing of all reported Dindo scores grade III or higher will be generated along with all complications reported on the corresponding form(s) and visit(s) and manually reviewed internally to ensure that the open-text specified complication corresponding to the reported Dindo score is reported as evident (i.e. response of "AE", "SAE") on the complication table(s). In addition, a masked data review by the AE Adjudication Committee will be performed to ensure that all reported Dindo scores of grade III and above are reasonable for the specified complication.
Indicator of excessive granulation tissue after 12 weeks	CRF-10, AE log	Binary	after 12 weeks through last visit	Through the timepoint of follow-up, based on the systematic collection of open-ended adverse events as reported on the AE log with an onset start date 12 weeks after the date of surgical intervention and based on the specific complications as reported on the evaluator (blinded) follow-up CRF-10 collected in 6-month intervals through 5 years, the indicator is defined as follows:
				1 = Yes, if granulation tissue is reported as evident (i.e. response of "AE", "SAE") on any of the complication tables as described above or on the AE log identified by the

				MedDRA coded preferred term "excessive granulation tissue" (case insensitive)
				0 = No, else if subject attended at least one post-operative visit 6 months or after and complication(s) of interest specified above are reported as "Not Evident" across all attended post-operative visits. Subjects with missing responses are included as long as the subject has at least one "Not Evident" response (assuming low missing response rate among attended visits).
				. = Missing, otherwise

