				0 = No, else if subject attended at least one post-operative visit immediately following surgical intervention or after and complication(s) of interest specified above are reported as "Not Evident" across all attended post-operative visits. Subjects with missing responses are included as long as the subject has at least one "Not Evident" response (assuming low missing response rate among attended visits).
				. = Missing, otherwise
				*Note: During masked review prior to final database lock, a listing of all adverse events on the AE log will be generated with AE verbatim terms mapped to a MedDRA coded preferred term and system organ class and manually reviewed by a clinical investigator to identify all AEs that may be a neuromuscular disorder. These AEs will be identified either by their MedDRA coded preferred term(s) or the verbatim term(s). If needed, a detailed listing of the manually identified AEs will be generated with details from the AE log including onset date, end date, grade, attribution, serious indicator, outcome, and comments and manually reviewed by a clinical investigator to identify all AEs that are a neuromuscular disorder.
Indicator of vaginal scarring after 12 weeks	CRF-10, AE log	Binary	after 12 weeks through last visit	Through the timepoint of follow-up, based on the systematic collection of open-ended adverse events as reported on the AE log with an onset start date 12 weeks after the date of surgical intervention and based on the specific complications as reported on the evaluator (blinded) follow-up CRF-10 collected at 6-weeks and in 6-month intervals through 5 years, the indicator is defined as follows:

				1 = Yes, if vaginal scarring is reported as evident (i.e. response of "A F" "C A F") are served as evident (i.e. response of
				"AE", "SAE") on any of the complication tables as described above or on the AE log identified by the MedDRA coded preferred term "vulvovaginal injury" (case insensitive) and the AE verbatim term containing "scar" (case insensitive)
				0 = No, else if subject attended at least one post-operative visit 6 months or after and complication(s) of interest specified above are reported as "Not Evident" across all attended post-operative visits. Subjects with missing responses are included as long as the subject has at least one "Not Evident" response (assuming low missing response rate among attended visits).
				. = Missing, otherwise

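### Four after-12-weeks safety indicators name CRF-10 as their only examination form, although the SAP elsewhere ties CRF-10 to the 6-week visit, and their 12-week limit is not applied to form data

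*SAP*

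**What the plan says.** SAP 10.2 defines four indicators for the period from 12 weeks to the last visit. Each lists CRF-10 and the AE log as its sources.

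- Excessive granulation tissue and suture exposure use the blinded evaluator's "follow-up CRF-10 collected in 6-month intervals through 5 years".
- Vaginal scarring and vaginal shortening use the blinded evaluator's "follow-up CRF-10 collected at 6-weeks and in 6-month intervals through 5 years".

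In all four rows the indicator is Yes if the event is marked as an AE or SAE on the form's complication table, or if a matching term appears on the AE log. The condition that onset be at least 12 weeks after surgery is attached to the AE-log entry only. A No requires attendance at a visit at 6 months or later and no contrary finding at any attended visit. Missing responses are tolerated if at least one response is negative.

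The visit schedule (Protocol Table 5, repeated in SAP 4.5) has two separate evaluator assessments: one headed "6 Week Unmasked Evaluator" at 6 weeks, and a masked one, with POP-Q and complications, at each visit from 6 to 60 months.

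**The concern.** An indicator of late events has to read the examinations at which late events are found. If CRF-10 is the 6-week form, these rows point the programmer to the one examination that lies outside the stated period and leave out the form that covers it. Non-events would be affected too. A participant with a clear 6-week form and any later visit could be coded No whatever the later examinations showed, unless the AE log said otherwise.

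The second problem runs the other way: an early finding at the 6-week visit can be counted as late.

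All four indicators are compared between arms (SAP 10.3), and scarring and shortening are named safety outcomes in Protocol L.2. Suture types and placement differ by procedure (Protocol J.2 to J.4), so neither error need fall equally on the three arms.

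**Working it through.** No plan figure is involved, so the check is a comparison of form sources across the SAP.

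**Which visit does each form belong to?**

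| Place | What it indicates |
|---|---|
| SAP 10.2, maximum Dindo score, evaluator forms: "evaluator (blinded) follow-up CRF-10/12 collected during surgery, during hospitalization, and at 6- weeks and in 6-month intervals through 5 years respectively" | CRF-8 and CRF-9 take surgery and hospitalization; CRF-10 and CRF-12 then match 6 weeks and 6-monthly, in that order |
| Same row, coordinator forms: "coordinator post-operative CRF-11, and coordinator follow-up CRF-13 collected at 6-weeks, and in 6-month intervals through 5 years respectively" | The parallel pair: CRF-11 at 6 weeks, CRF-13 6-monthly |
| SAP 10.2, prolapse mesh erosion: "follow-up CRF-10/12 collected at 6-weeks and in 6-month intervals through 5 years" | The two evaluator forms are again named together for the two schedules |
| SAP 9.3, POP-Q items from 6 to 60 months: "evaluator (blinded) follow-up CRF-12 during POPQ examination" | CRF-12 is the masked examiner's form from 6 months on |
| Protocol Table 5 | One evaluator assessment at 6 weeks and one type from 6 months on, with no second evaluator form at the later visits |

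Together these point to CRF-10 as the 6-week form and CRF-12 as the 6-60 month form.

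**What do comparable rows do?** Five other after-12-weeks indicators (suture erosion, pelvic pain, daily pelvic pain, vaginal infection or discharge, vaginal bleeding) use CRF-13 and the AE log, and omit the 6-week coordinator form CRF-11. The evaluator counterpart of CRF-13 is CRF-12. Of the four rows at issue, 4 list CRF-10, 0 list CRF-12 and 4 list the AE log.

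**How much examination data is at stake if the form number is followed?** SAP 4.1 gives follow-up of 36 to 60 months with 6-monthly visits, which is 36/6 = 6 to 60/6 = 10 scheduled masked examinations per completing participant. On the reading above, form data would come from the 6-week examination instead of those 6 to 10.

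**What would the AE log still supply?** After 6 months it takes deaths, and events of grade II or higher judged at least possibly related to the pelvis or surgery (SAP 10.2, reportable adverse events; Protocol N.5). The entry must also match the row's coded or verbatim term. Milder or differently worded examiner findings would drop out. The pre-lock query in SAP 7.5 covers exposures and erosions only and checks that AE-log entries also appear on a complication table. It does not carry examiner findings to the log.

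**Does the 12-week limit reach the form data?** It does not. In the scarring and shortening rows the form schedule expressly includes 6 weeks, and nothing removes those findings. This holds whatever CRF-10 turns out to be. For granulation tissue and suture exposure it follows only if CRF-10 is the 6-week form. The Dindo row shows the intended handling: it drops granulation tissue, suture exposure and suture erosion recorded up to 12 weeks, and names the surgery and 6-week visits as those excluded.

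**The case against.** The strongest reply is that the rows, read whole, already direct the programmer to the later examinations. Two of them give a 6-monthly schedule and all four call the evaluator blinded, whereas the 6-week evaluator is unmasked. The stated period starts after 12 weeks, and a No needs a visit at 6 months or later. On that view only the form number is wrong. Nor is the identity of CRF-10 settled: the scarring, shortening and neuromuscular rows give it both schedules, the incontinence rows in SAP 9.3 attach 6 weeks to CRF-12 and CRF-13, and the CRFs themselves are not in the documents.

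There are also partial safeguards. The AE log sets each indicator independently. The Dindo outcome reads both evaluator forms through 5 years. Vaginal length from CRF-12 is reported at every 6-month visit, and Protocol L.2 defines shortening by that length. The masked data review tabulates complications before lock. Secondary tests are descriptive and unadjusted for multiplicity (SAP 7.7).

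Much of this stands. A reader might infer that the 6-60 month examinations are never read and that all examiner-found events are lost. The documents do not support that: no statement confines CRF-10 to 6 weeks, the rows describe 6-monthly collection, and the AE log remains a source. What the reply does not remove is the contradiction itself, since form number and schedule disagree and a program has to follow one of them. The safeguards are incomplete. The Dindo outcome takes one score, for the most severe complication, and does not identify scarring or shortening. SAP 9.3 analyses vaginal length as a continuous measure without the 6 cm cut. The reply also does not meet the missing 12-week limit on form data, where the row titles show the intent but the rule does not carry it out.

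**Conclusion.** The point holds in two parts of different strength.

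1. **Form source.** The four rows contradict the rest of the SAP on which evaluator form feeds them, and CRF-12 is apparently missing. Late examiner findings that did not reach the AE log could be missed. This is conditional on CRF-10 being the 6-week form and on programs following the number. The size is unknown, because the documents do not say what share of examiner findings was also logged.
2. **12-week limit.** For scarring and shortening, as written, 6-week form findings count as after 12 weeks. This does not depend on identifying the form. The number of such findings is also unknown.

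Both bear on prespecified secondary safety comparisons. The primary outcome and its hypothesis tests are unaffected. The correction should be made because it is specific and nearly free.

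**What to change.** - Check the annotated CRFs and name the 6-60 month evaluator form, apparently CRF-12, in the granulation tissue, suture exposure, scarring and shortening rows, in both the source column and the definition. If CRF-10 was in fact used after 6 weeks, say so and reconcile the Dindo and mesh rows instead.
- Add one sentence to SAP 10.2 excluding findings on the 6-week form from every indicator titled after 12 weeks, as the Dindo row already does for granulation tissue and suture exposure. Delete the reference to 6-week collection from the scarring and shortening rows.
- Confirm which form the analysis programs read. If they read only the 6-week form, rerun the four indicators and record the change in SAP section 12.

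The cost is short edits to four definitions, one added sentence and a program check. No new data are needed.
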